VC sessions are provided remotely by the child's therapist from the clinic. Parents who do not have the necessary equipment for VC will be provided notebook computers and omnidirectional microphones. The MOHH commissioned VC platform will be used for observing the home session and coaching parents. Parents will orient the computer's web cam to the selected activity area in the home while using the wireless headset for communication. An omnidirectional portable microphone will be placed in the vicinity of the routine home activity so that the therapist can look, listen and understand the dynamics of parent child interactions clearly during a given daily routine involving the child.

Telerehab sessions will follow the ethical and practice guidelines of computer-mediated intervention including online communication, consent, confidentiality & privacy and security issues, verbal and nonverbal feedback.

Strategies: Parents will be trained in using evidence-based strategies (e.g., follow your child's lead, imitation & modelling, communicative temptations, playful obstructions) during playtime activities and daily routine.

Approach: Intervention sessions will be provided by therapists trained in the FSC and the parent coaching protocol. Parent-child interactions during activities at home will be observed through the VC platform commissioned by MOHH. Parents will be encouraged to interact with their child using strategies aimed at increasing their child's attention and motivation, turn-taking routines, initiating and responding to joint attention, communication, etc. Sessions will follow the collaborative practice protocol. The protocol provides an outline for the session structure (i.e. checking in, reviewing, observation, reflection, explanation and coaching of new topics and strategies, setting goals and follow-up planning in the home context and closing).

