
g. Is the tele-health intervention more cost-effective than
	
Total direct and indirect costs from health system and societal perspective
	
Total direct and indirect costs from health system perspective: Total intervention costs, including development costs, cost of using the videoconference platform, labour and infrastructure as well as total medical costs and costs of other interventions incurred by parents as related to ASD. Costs related to the evaluation alone will be excluded.
	
Compare total direct and indirect costs from baseline to program conclusion from health system and societal

the standard care?		Total direct and indirect costs from societal perspective: As above and also including cost of travel and productivity losses incurred by parents.	perspective between two intervention groups
h. Is the tele-health intervention effective in improving parents' implementation of intervention strategies?	NDBI (Naturalistic Developmental Behavioural Interventions)-Fi	NDBI-Fi is an 8-item observational rating scheme that evaluates caregiver implementation of common strategies from treatments classified as NDBI based on short videos of caregiver-child interactions.	Change on the NDBI-Fi will be calculated by tracking the changes on individual items and average rating from baseline to program conclusion for participants in the telerehab arm

Quantitative process indicators (the outputs indicated in the logic model) will be assessed in the intervention group as well as part of monitoring and process evaluation.

The qualitative research questions will enhance our understanding of both the impact and process-related outcomes, using semi-structured interview guides. Parents will be asked about perceived effectiveness, engagement and stress, as well as their ability to cope financially with treatment. At baseline, we will also investigate attitudes/perceptions towards telerehab, and factors that affect willingness to take up telerehab. At the end of the study, while the scope of the quantitative evaluation is limited, we will explore parent experiences, satisfaction and concerns, and perceptions of sustainability and future care plans.

Data Collection Plan

Recruitment

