To examine cost-effectiveness, we will compare resource utilization between treatment and control groups to estimate resource and cost differences in absolute terms from the direct medical cost perspective as well as the societal perspective (inclusive of the direct costs of travel and the indirect cost of parental time). As the trial focuses on non-inferiority, the assessment of cost-effectiveness will rely on whether the intervention is cost-saving relative to the standard of care. We will also perform modelling estimates to quantify the uncertainty surrounding the incremental cost-effectiveness ratio.

Methodology

Decision Problem

Objective

To assess the cost-effectiveness, in terms of incremental cost effectiveness ratio (ICER) of the **tele-health (telerehab) mode** of delivering the early intervention (EI) in children with

Autism Spectrum Disorder (ASD) relative to the **standard care** (clinic-based sessions only) in costs and outcomes as measured by Mullen Scales of Early Learning (MSEL), Vineland Adaptive Behavioural Composite score (VABS) and Joint Engagement Rating Inventory (JERI).

$$ICER = \frac{Costs_{New} - Costs_{Old}}{Effects_{New} - Effects_{Old}}$$

Figure 1: Incremental cost-effectiveness ratio (ICER), calculated by the difference in cost between two possible interventions, divided by the difference in their effect.

Target Population

The study target population for these analyses will be the children assessed to fulfil the inclusion criteria of the Telerehab RCT from NUH CDU. The delivery of early intervention heavily involves a caregiver, often the biological parent(s) of the children receiving therapy for early intervention.

Study Perspective

The study will take on a **societal perspective**. This includes healthcare costs from the provider’s perspective, non-healthcare costs incurred by the patient from social care and child care, as well as productivity losses for the patient’s caregiver.

The time horizon of the study includes the cost incurred and benefits from the entire program duration, from enrolment to the final review.

Comparator – Standard Care

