Health sector cost will be primarily attributed to the cost of treatment delivered by the institution, NUH CDU. The gross charges for paediatrician review, IIP review and administering surveys and assessments for the children are consistent in both study arms. Only variable cost between both study arms will be included. The variable cost includes the clinic-based intervention charges and video-conferencing-based intervention charges across both arms. The assumption for health sector cost will be that participants from both arms attend all the review and assessment sessions as they are essential to the intervention plan. The only variability would be attributed to defaulted therapy sessions.

Direct Non-Healthcare Costs

Transportation Costs

Transportation cost will be estimated using the responses from the baseline cost survey administered to caregivers. The total transport cost per study arm (standard vs telerehab) will be calculated by multiplying the *observed number of clinic-based visits* (accounting for missed appointments/therapy sessions) with the average cost of transportation indicated by the caregiver multiplied by two to account for round-trip travelling.

Caregiver and other care costs

Costs from other sectors include care cost from attending courses, hiring domestic helpers and/or other forms of care support for the child. This information is obtained from the cost survey administered to the parents.

Indirect Costs

Productivity Loss

Productivity loss will be calculated using the human capital approach. The human-capital method takes the patient's perspective (in this case the parent's time) and counts any hour not worked as an hour lost.

² <https://yhec.co.uk/glossary/probabilistic-stochastic-sensitivity-analysis/>
TRAutism HSDP Protocol_Version 8_19/08/2022

Productivity loss in this study will be primarily attributed to the caregiver taking time off from work to attend treatment with the patient (their child) and applying intervention strategies with the child. The time spent by caregivers includes the following:

- i. time spent on travelling CDU for treatment (two-way trip);
- ii. time spent on therapy sessions (30mins for video-conference, 45mins for clinic-based);
- iii. employment charges

Outcomes

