We will examine the primary outcome, Mullen's Scale of Early Learning (MSEL) Early Learning Composite Score (ELC) as the key outcome of interest (i.e. the denominator for ICER). We will also examine the outcomes in VABS and JERI as outcomes of interest. Parameters for modelling for outcomes will be obtained from analyses specified in the previous section.

Input Data for Outcomes and Cost Data for the Model

The input data for the model from the survey administered is listed below in Table 2.

Table 2: Data Source and Parameters Estimates and Distribution for Cost-effectiveness Analysis

	Standard	Telerehab	Parameters Estimated	Distribution
Outcomes	Estimates from analysis from t-test/regression for: MSEL-ELC, VABS composite score and/or JERI	Estimates from analysis from t-test/regression for: MSEL-ELC, VABS composite score and/or JERI	Mean (SD) improvement in outcomes examined	Normal
Direct Healthcare Cost				
Attendance for therapy sessions	Number of clinic-based therapy sessions attended	Number of clinic-based and telerehab therapy sessions attended Telerehab consists of clinic-based sessions at the start of the program + telerehab sessions	Mean (SD) of therapy session attended across each study arm	Normal or gamma
Healthcare cost	Total cost of clinic-based therapy sessions	Total cost of clinic-based + telerehab therapy sessions	Number of visits * fixed cost per visit (standardized for FY2021/22)	Fixed
Direct Non-healthcare Cost				
Transport costs	Survey questions 
 • What mode of transport did you use to get here today? • How much did it cost? • Do you usually use this mode of transport to get to the clinic/CDU? • If no, what is your usual mode of transport? • How much did it cost? 	Survey question 
 • What mode of transport did you use to get here today? • How much did it cost? • Do you usually use this mode of transport to get to the clinic/CDU? • If no, what is your usual mode of transport? • How much did it cost? 	The total transportation cost incurred by participants will differ between study arms by nature of the mode of delivery. The actual transportation cost will account for two-way (round trip) and the observed visits (accounting for missed appointments for example)	Normal

			Transport Cost = Total no. of trips * Mean transport cost * 2	

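### Health-sector cost is defined in two incompatible ways, and the costing method has no line for platform, development and equipment costs that arise only in telerehab

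*Combined protocol and SAP*

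**What the plan says.** Row g of the Indicators and Outcomes table sets the health-system cost to be compared between arms: "Total intervention costs, including development costs, cost of using the videoconference platform, labour and infrastructure as well as total medical costs". It names a single exclusion: "Costs related to the evaluation alone will be excluded".

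The section Direct Healthcare Costs, Health sector cost, is narrower. It says "Only variable cost between both study arms will be included", and describes the content of that cost as follows: "The variable cost includes the clinic-based intervention charges and video-conferencing-based intervention charges across both arms". On what can differ between participants it adds: "The only variability would be attributed to defaulted therapy sessions". Table 2 turns this into the formula "Number of visits * fixed cost per visit (standardized for FY2021/22", with the distribution given as fixed. Table 2 has no row for platform, development, equipment or infrastructure.

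Under Intervention: Telerehab Program, the plan states: "Parents who do not have the necessary equipment for VC will be provided notebook computers and omnidirectional microphones". Under Cost-Effectiveness Analysis, it says that "the assessment of cost-effectiveness will rely on whether the intervention is cost-saving relative to the standard of care". Study Perspective adopts a societal view in which healthcare cost is taken from the provider's side.

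**The concern.** The two places answer the same question differently. An analyst who follows row g will cost the programme. An analyst who follows the costing section and Table 2 will multiply attended sessions by a tariff.

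The costing section's own rule does not support the narrower content. It keeps what varies between arms. Platform use, development of the telerehab service and equipment supplied to families are present in one arm and absent in the other, so they vary between arms by construction.

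The economic conclusion rests on whether telerehab saves money. If the session charge does not recover these items, leaving them out lowers the telerehab total only and could make a cost increase look like a saving. The planned sensitivity analyses would not show this, because an item with no input row cannot be varied and the per-visit cost is held fixed.

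**Working it through.** **Inputs from the documents.** Table 1 gives standard care 16 clinic sessions (45 + 15 min each). Telerehab has 2 clinic sessions (45 + 15 min) and 16 video sessions (30 + 15 min). Annex 1 agrees on the counts: 6 + 4 + 6 = 16 clinic sessions in standard care; 2 clinic and 4 + 4 + 2 + 6 = 16 video sessions in telerehab.

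**Reproducing Table 1.**
- Standard: 16 × 45 = 720 and 16 × 15 = 240, total 960 min.
- Telerehab: 2 × 45 + 16 × 30 = 570 and 18 × 15 = 270, total 840 min.

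Both match the plan. The difference is 960 − 840 = 120 booked minutes per child, or 120/960 = 12.5%.

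**Inputs not in the documents.** There is no price for either type of session and no figure for platform, development, equipment or infrastructure. I take one clinic-session charge as the unit and assume that a video session is charged at r units, with r from 0.5 to 1. I also assume full attendance.

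**Charges-only result (the Table 2 formula).** Standard costs 16 and telerehab costs 2 + 16r. The saving per child is 16 − (2 + 16r) = 14 − 16r.

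| r | Telerehab | Saving per child, in clinic charges | Saving as share of 16 |
|---|---|---|---|
| 0.5 | 10 | 6 | 37.5% |
| 0.667 (30/45, contact time) | 12.67 | 3.33 | 20.8% |
| 0.75 (45/60, booked time) | 14 | 2 | 12.5% |
| 0.875 | 16 | 0 | 0% |
| 1 | 18 | −2 | −12.5% |

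**Adding what is left out.** Let m be the net omitted cost per child, telerehab minus standard, in the same unit. The health-sector saving becomes 14 − 16r − m, so a positive charges-only saving is reversed when m exceeds 14 − 16r. At r = 0.75 the threshold is two clinic charges per child. As a programme total, that is 2 × 100 = 200 clinic charges spread over the 100 children planned for the arm, or 2 × 66 = 132 over the 66 that the sample-size calculation needs.

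**Sign of m.** Platform, development and supplied equipment push m up. Labour and infrastructure not already in the charge could push it down, because standard care books 120 more minutes and uses 16 clinic sessions against 2. The documents do not allow m to be computed.

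**The case against.** The strongest reply is that nothing has been shown to be missing. The plan never says what a per-visit charge covers. It may already recover therapist time, overheads or a platform fee, and adding these again would double count. That stands, and it limits any claim about the size of the effect. It does not remove the conflict between the definitions.

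Second, the costing section calls treatment cost the primary part and says that variable cost includes session charges, so its list need not be complete. Data Collection Time Points also plans to record hospital resource use. This leaves slight room for other items, but Table 2 has a healthcare-cost row and gives no input for them.

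Third, a reader might infer that all the row g items fall on telerehab, so that the plan is biased in its favour. The documents do not support this. Labour and infrastructure arise in both arms, and Table 1 points to a higher labour cost in standard care. That labour gap is itself uncertain: Annex 1 lists 30 minutes of telerehab-only video preparation and observation at baseline, and a 30-minute video observation at final review, which Table 1 does not count. Some of that time may serve only the evaluation.

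Fourth, the break-even concerns health-sector cost only. The societal analysis adds transport, travel time and parental session time, and telerehab has 14 fewer clinic intervention sessions, so the societal threshold may be higher. This stands.

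Finally, row g does not name equipment, and development comes before enrolment whereas Time Horizon starts at enrolment. Both need a decision in the plan. Neither justifies silence.

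**Conclusion.** The inconsistency is certain: row g and the costing section with Table 2 define health-sector cost differently, and the difference bears on the cost-saving test. Platform, development and supplied-equipment costs belong in the comparison even under the variable-cost rule. Omitting them favours telerehab unless the session charge contains them.

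The net direction and size are not established. It would be tempting to read the gap as proof that a telerehab saving will be spurious, but that needs prices, the content of the charge, and labour and infrastructure costs in both arms, none of which the documents give. The figure of two clinic charges per child holds only for r = 0.75, full attendance and health-sector cost alone. Over the assumed range of r, even the sign of the charges-only result changes. The primary clinical comparison is not affected.

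**What to change.** Amend the Health sector cost section and Table 2 so that both arms follow row g:

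- State what the FY2021/22 per-visit cost covers.
- Add rows for any platform, supplied-equipment and development cost that it does not cover.
- Cost labour and infrastructure in both arms where the charge does not already include them, so that the correction is neither one-sided nor double counted.
- State how development cost is allocated per child, and reconcile this with Time Horizon and with row g's own baseline-to-conclusion window.
- Vary these items in the one-way and probabilistic sensitivity analyses.
- Use this as the base case and report the charges-only result as a sensitivity analysis.

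The cost is a change of wording, retrieval of programme cost figures and some extra analysis. No new patient data are needed. Telerehab may look less favourable as a result.

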The current standard program for early intervention treatment is in-clinic therapy based on the **Foundational Skills Curriculum (FSC)**: a framework for early intervention developed from outcomes of an Autism research project conducted in the UK. This framework provides a clear and systematic approach to understanding the child's functioning in 3 core areas of development (across 141 items): Play, Social Interaction, and Communication.

The telerehab program will provide parent coaching on EI through video conferencing using the FSC. The telerehab program aims to improve access to services and facilitate intervention in the natural environment of children and their families by developing video conferencing (VC) as a feasible and acceptable medium to build parent capabilities in EI. The specific service model objectives are to realize positive gains in service efficiency (i.e. reducing the total time and resource utilization per completed intervention course relative to current practice); reduce total costs and non-financial barriers for patients (i.e. access) as well as the total cost to the health system per completed course (i.e. sustainability) and realize positive gains in provider productivity and hence cost-effectiveness (i.e. reduced cost per unit outcome achieved).

Implementation Strategies and Patient Flow

CDU receives referrals from polyclinics for children at risk of ASD. These referrals will be scheduled for a developmental assessment by the developmental paediatrician. Baseline assessments will be conducted under the program as well as under standard care. Children who are enrolled into the evaluation study will then continue with either the standard program (clinic-based therapy) or the telerehab program. The program schedule for the patient in terms of type of visits and intervention blocks for both the standard program and telerehab is shown in Annex 1: Program Schedule. The duration of clinic-based intervention sessions will be 60 min while the duration of VC based intervention sessions will be 45 min.¹

Baseline Assessments

Visit 0/1: Child found to be at risk for ASD on clinical evaluation by the developmental paediatrician based on the DSM-5 criteria will be referred for this study. The informed consent will be obtained prior to undergoing any research-related activities.

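### Efficiency and sustainability are defined per completed course, but the plan costs only attended sessions, so missed sessions count as savings and the stated objective has no estimator

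*Combined protocol and SAP*

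**What the plan says.** Objectives and Trial Design commits the trial to evaluating efficiency and sustainability against standard care. Program Implementation defines them: efficiency is "reducing the total time and resource utilization per completed intervention course relative to current practice", and sustainability is "the total cost to the health system per completed course (i.e. sustainability".

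The costing is built differently. Health sector cost includes only the charges that differ by arm and assumes that "participants from both arms attend all the review and assessment sessions as they are essential to the intervention plan". It then states: "The only variability would be attributed to defaulted therapy sessions". Table 2 takes as its attendance parameter the "Mean (SD) of therapy session attended across each study arm" and computes healthcare cost as "Number of visits * fixed cost per visit (standardized for FY2021/22". Transportation Costs likewise uses observed clinic visits, "accounting for missed appointments/therapy sessions".

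The decision rule is in Cost-Effectiveness Analysis: "the assessment of cost-effectiveness will rely on whether the intervention is cost-saving relative to the standard of care". The same part of the plan gives an ICER as its formal objective. Its target population is children who meet the inclusion criteria, and it does not say whether costs are restricted to the per-protocol set.

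**The concern.** An objective stated per completed course needs completed courses in the denominator, with the resources spent on families who did not finish in the numerator. The planned costing has neither. Each missed session removes its whole cost from the arm, so non-attendance counts towards a cost-saving verdict.

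Unequal completion is foreseeable. Sample Size Calculation raises 132 to 200 for losses, and the plan expects some transfers to other services before the program ends. Annex 1 is also asymmetric: the standard arm finishes its sessions in block 3, while telerehab still has 6 of its 18 in block 4. A family leaving after block 3 has used 960 of 960 scheduled minutes in the standard arm but 570 of 840 in telerehab. Attended-session costing would show that pair as a 41% telerehab saving (1 − 570/960), against 12.5% for two full courses.

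**Working it through.** **Inputs.** Session counts and lengths come from Table 1 and Annex 1. The documents give no charges, so scheduled minutes stand in for cost (assumption). Attendance, loss rates and time of leaving are also assumptions. The value 34% is the trial-wide recruitment allowance, 1 − 132/200, not a forecast for either arm.

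**The plan's own figure.** Standard: 16×45 + 16×15 = 720 + 240 = 960 min. Telerehab: (2×45 + 16×30) + 18×15 = 570 + 270 = 840 min. Both match Table 1. At full attendance telerehab is 1 − 840/960 = 12.5% cheaper on either measure.

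**Missed sessions only.**
- Standard 80%, telerehab 100%: 0.8×960 = 768 v 840, so telerehab is 9.4% dearer.
- Standard 100%, telerehab 80%: 960 v 0.8×840 = 672, so telerehab is 30.0% cheaper.
- Both 90%: 864 v 756, still 12.5% cheaper.
- Break-even against full telerehab attendance: standard at 840/960 = 87.5%.

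A per-protocol restriction at 80% does not remove this. A control child with 13 of 16 sessions passes (0.8×16 = 12.8) and costs 13×60 = 780 min, against which a full telerehab course is 7.7% dearer (840/780).

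**Families leaving.** Let F be the full course (960; 840), P the minutes used by a leaver after block 1 (6×60 = 360; 2×60 + 4×45 = 300) and d the proportion lost. Cost per randomised child is C = (1 − d)F + dP. Cost per completed course is C/(1 − d).

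| Loss, standard / telerehab | Per randomised child, min | Telerehab v standard | Per completed course, min | Telerehab v standard |
|---|---|---|---|---|
| 34% / 34% | 756 v 656 | −13.2% | 1145 v 995 | −13.2% |
| 20% / 34% | 840 v 656 | −21.9% | 1050 v 995 | −5.3% |
| 10% / 34% | 900 v 656 | −27.1% | 1000 v 995 | −0.5% |
| 20% / 48% | 840 v 581 | −30.9% | 1050 v 1117 | +6.4% |
| 34% / 20% | 756 v 732 | −3.2% | 1145 v 915 | −20.1% |
| 34% / 10% | 756 v 786 | +4.0% | 1145 v 873 | −23.8% |

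For the fourth row: 0.8×960 + 0.2×360 = 840 and 840/0.8 = 1050; 0.52×840 + 0.48×300 = 580.8 and 580.8/0.52 = 1117.

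At equal loss the between-arm ratio is the same on both measures, because both arms are divided by the same proportion. The absolute gap differs: 100 min per randomised child, 151 per completed course.

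**How large a gap changes the sign.** Per randomised child, with telerehab loss of 10% or 20%, the arms are equal when standard loss is (960 − 786)/600 = 29% or (960 − 732)/600 = 38%. Per completed course, with standard loss of 20%, they are equal when 840 + 300×d/(1 − d) = 1050, so d = 0.7/1.7 = 41%. These are gaps of about 20 percentage points. Later leaving moves the threshold: if families leave after block 2 (600 and 480 min), 10% v 34% gives 924 v 718 per randomised child (−22.3%) but 1027 v 1087 per completed course (+5.9%).

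**The case against.** Costing observed use per enrolled child is a legitimate measure, and the economic section's own objective is an ICER. That stands as a reason to keep both. It does not withdraw the objectives in Program Implementation, and the ICER uses the same attended-session costs.

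The sentence on variability concerns defaulted sessions, not lost families. The only analysis set the plan names is per-protocol, which excludes children below 80% of sessions. On that set every leaver modelled above disappears. This also stands: one cannot say that dropouts will lower an arm's cost, only that the set is unnamed. But restricting costs to completers would not supply the missing measure, because it discards what was spent on leavers. With full attendance among completers it would show 12.5% in every row, including the one where telerehab is 6.4% dearer per completed course.

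There are mitigations. Make-up sessions are offered (described for the standard program), a child moves on only after finishing the previous phase, and number of visits is a parameter in the probabilistic sensitivity analysis. These reduce missed sessions or describe their uncertainty, but do not change what is estimated. Some early exits may be planned transfers rather than poor retention, which argues against making cost per completer the main result.

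A reader might infer that whichever arm loses more families will come out cheaper, or that the plan's conclusion will be reversed. The documents support neither. At 34% / 20% the standard arm loses more families and still costs more (756 v 732), and nothing in the documents predicts gaps in loss large enough to change the sign.

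**Conclusion.** The mismatch is in the text: two stated objectives are defined per completed course and no planned analysis estimates them. Under the cost-saving rule, missed sessions make an arm look cheaper than a completed course costs, and so do early leavers if they are in the cost analysis set.

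The distortion is nil at full attendance, and nil in the between-arm ratio at equal proportional attendance or equal loss. It grows as attendance or completion diverges by arm. A difference of 20 percentage points in attendance moves a 12.5% saving to a 9.4% excess or to a 30.0% saving. With loss after block 1, a change of sign needs a gap of roughly 20 points; smaller gaps change the size but not the direction.

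All of these figures rest on scheduled minutes as a proxy. Actual percentages depend on the charge for a video session relative to a clinic session, and transport and productivity costs are not included.

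**What to change.** 1. State that costs are analysed for all randomised children, and that leavers' costs are not dropped through the per-protocol set.
2. Keep cost per randomised child. Beside it, report for each arm the total cost of all randomised children divided by the number who completed the course, with a bootstrap confidence interval for the between-arm ratio.
3. Define completion. Protocol Deviation and Per-protocol Analysis illustrates the 80% rule with 8 of 10 control sessions, while the standard program description, Table 1 and Annex 2 give 16. These must be reconciled before the denominator can be counted.
4. Add one sensitivity analysis that charges every defaulted session at its scheduled therapist time (60 min clinic, 45 min video). This covers missed sessions among children who still count as completers, which item 2 alone does not. It is an upper bound and needs no record of whether the slot was refilled. It also fits the cost indicator in Indicators and Outcomes, which includes labour and infrastructure that may be incurred when a family does not attend.

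The cost is analysis wording: the plan already uses attendance and a fixed cost per visit. The drawback is a ratio measure that gives partial courses no credit, so it should supplement, not replace, cost per randomised child and the ICER.
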